1.0 Study Summary

Study Title	Neonatal Esophagus and Airway Interactions in Health and Disease: Mechanisms and Management of Infant Dysphagia
Study Design	Single arm observational study
Primary Objective	Our overall aims are to identify novel diagnostic aerodigestive targets, define effective therapeutic interventions, and advance the mechanistic basis of therapeutic outcomes-i.e., full oral feedings.
Secondary Objective(s)	
 1) Examine the differences in outcomes among preterm born vs. full term born 2) Examine the differences in outcomes among those with normal versus abnormal VFSS
Research Intervention(s)/Investigational Agent(s)	Providing esophageal manometry concurrent with video fluoroscopy swallow study (VFSS) in order to determine sensory-motor dysphagic mechanisms which will better inform treatment options
IND/IDE #	N/A

PROTOCOL TITLE: Neonatal Esophagus and Airway Interactions in Health and Disease: Mechanisms and Management of Infant Dysphagia

Study Population	
All infants will have a diagnostic VFSS scheduled.
 
Inclusions: Infants with feeding-related aerodigestive symptoms who are \leq 60 weeks PMA (both pre-term and full-term) who are orally feeding $\geq 25\%$ of at least 50% of their feeds who are on full enteral feeds with no more than 1LPM NC respiratory support.
 
Exclusions: Genetic or metabolic syndromes, IVH grade III or greater, moderate to severe HIE, craniofacial, airway or foregut malformations or ENT or neuro surgeries. Infants who are exclusively breastfeeding are also excluded.

Sample Size	60
Study Duration for individual participants	Up to 4 weeks (initial manometry study with diagnostic VFSS, repeat manometry at 4-6 weeks as relevant), will follow feeding outcomes and growth and developmental outcomes for 1 year
Study Specific Abbreviations/ Definitions	
VFSS video-fluoroscopy swallow study
 
LP laryngeal penetration
 
LA laryngeal aspiration

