6.0 Procedures Involved*

6.1 Study Design

- Study design and setting: Eligible subjects (study) will undergo diagnostic VFSS in combination with manometry, either concurrent or sequential. They will have parental choice of preferred feeding therapy. The data is from single center prospective observational study. The controls are those who had VFSS alone with provider recommendations from the same single center.
- Patient population and characteristics: (i) Study and control infants have oral feeding difficulties with symptoms requiring interventions/monitoring. (ii) They have diagnostic need for VFSS due to aerodigestive and feeding difficulties. (iii) Study subjects must have a signed informed consent from parent/legal guardian prior to manometry study. Control subjects did not require consent as they were historical controls.
- Inclusion criteria: Infants with feeding-related aerodigestive symptoms who are \leq 60 wks PMA (both pre-term and full-term) who are orally feeding \geq 25% of at least 50% of their feeds who are on full enteral feeds with no more than 1LPM NC respiratory support. All infants will have a diagnostic VFSS scheduled.
- Exclusion criteria: Genetic or metabolic syndromes, grade III or greater, moderate to severe HIE, craniofacial, airway or foregut malformations or ENT or neuro surgeries. Infants who are exclusively breastfeeding are also excluded.
- Test-1: VFSS with concurrent or sequential pharyngo-esophageal manometry along with standard safety metrics. Esophageal and pharyngeal provocation induced

PROTOCOL TITLE: Neonatal Esophagus and Airway Interactions in Health and Disease: Mechanisms and Management of Infant Dysphagia

aerodigestive reflexes will be tested. Oral feeding challenge test is performed during manometry. The same procedures without VFSS will be repeated at Time-2 where feasible and relevant.

- Overall Study Endpoints: Primary endpoint is therapeutic success defined as full oral feeding without symptoms requiring intervention at 4 weeks (for outpatient studies and those still admitted at 4 weeks) or discharge, whichever is earlier. Secondary clinical end points include growth velocity and feeding outcomes at 1 year.
- Methods to overcome Potential Confounders: It is NICU standard to document in EPIC: i) Daily documentation of symptoms, medication use, feeding methods and duration, feeding volume and weight, ii) Weekly documentation of growth velocity (weight, length, head circumference).

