9.0 Inclusion and Exclusion Criteria*

- 9.1 All infants < 6 months PMA who are scheduled for a VFSS will be screened for the above eligibility criteria.
- 9.2 All subjects who consent and receive a concurrent or sequential VFSS and esophageal manometry will be included in the analysis.
- 9.3 Our population will include individuals who are not yet adults (infants)

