16.0 Data Management* and Confidentiality

16.1 Data Analysis Plan

- Descriptive statistics will be reported as median (IQR), mean \pm SD or total number and percentage for demographics and clinical characteristics. For PPG vs FOD historical control comparisons, two-sample t-test or ANOVA will be used for the continuous variables and chi-squared or Fischer's exact tests will be used for the categorical variables, whichever is appropriate. Non-parametric method (e.g. Wilcoxon) might be used if the data is not normally distributed. Normality will be assessed using Shapiro-Wilks test and visually inspection of the data. For other Normal vs Abnormal VFSS and the effect of parent preferred therapy -flow modification or thickener use) comparisons, due to the nature of the repeated measure of the data, repeated measure ANOVA for continues measured variables and Generalized estimating equation (GEE) for categorical variables, to predict the likelihood of the specific response, will be used as to make the between group comparisons. Compound symmetry (CS) will be specified for the covariance structure of the repeated data. Bonferroni correction will be used to conserve the overall type I error at $\alpha=0.05$. To characterize the association between the disease comorbidities and feeding success, simple and multiple logistic regression analysis will be performed. Statistical Analysis Software, version 9.4 (SAS Institute Inc., Cary, NC, USA)

- 16.2 Data will be stored in RedCap and each subject will have a file which is kept in a secured locked location.

- 16.3 Data will be verified by at least two individuals on the study team

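### Growth velocity has no stated unit, window or age standard, and the methods named for continuous outcomes do not adjust for age or size, so an imbalance in either would read as a growth difference

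*Combined protocol and SAP*

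**What the plan says.** Section 6.1, under the overall endpoints, states: "Secondary clinical end points include growth velocity and feeding outcomes at 1 year". The bullet on potential confounders in the same section adds "Weekly documentation of growth velocity (weight, length, head circumference" as part of routine NICU charting. It lists what is recorded and contains no statistical adjustment. Neither place gives a unit, an interval or a growth reference. Section 6.4 adds only that growth is followed to 1 year of age.

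On the population, section 6.1 admits infants up to "60 wks PMA (both pre-term and full-term) who are orally feeding" a minimum share of their feeds, with no lower age limit. Section 9.1 words the screening limit differently: "All infants < 6 months PMA who are scheduled for a VFSS will be screened".

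On the comparison groups, section 6.1 says "The controls are those who had VFSS alone with provider recommendations from the same single center". No matching on age, gestation or size is described. Section 1.0 also lists a secondary objective to "Examine the differences in outcomes among preterm born vs. full term born".

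On the analysis, section 16.1 says that for study against historical control "two-sample t-test or ANOVA will be used for the continuous variables", and that "Non-parametric method (e.g. Wilcoxon) might be used if the data is not normally distributed". For normal against abnormal VFSS, and for the parent-preferred therapies, it names repeated-measures ANOVA for continuous measures. No covariate is named for any continuous outcome. The only multivariable model is a logistic regression of feeding success on comorbidities, which does not cover growth. No test is named for preterm against full term.

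**The concern.** Growth rate in early infancy depends on age and size. None of the groups to be compared is formed by randomisation: the controls are historical, the VFSS groups are defined by a test result, and the therapy groups follow parental choice. Nothing in the design keeps them alike in PMA, gestational age or starting size. An unadjusted test on such an outcome mixes any effect of manometry-informed care or of therapy with whatever age difference is present. The error could run in either direction. It could suggest a growth benefit or harm where there is none, or hide a real one.

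The missing definition adds to this. Grams per day, grams per kilogram per day and change in z-score depend on age to very different degrees, and all fit the term growth velocity. Choosing among them, and choosing the window, after the data are seen would leave room for a selective result.

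**Working it through.** The documents give no figure for growth velocity to reproduce. The 90% power in section 3.3 concerns the feeding success rate and does not bear on this point.

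**Inputs from the documents.** 60 study infants (sections 1.0, 3.3 and 11.1); PMA up to 60 weeks; two-sided 0.05 (section 3.3, stated for the primary outcome); unadjusted two-sample test (section 16.1).

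**Assumptions, none of them in the documents.** Daily weight gain falls by b = 0.3 to 0.9 g/day per week of PMA (central 0.6). The SD at a given age is s = 8 g/day. Mean PMA differs by d weeks between the groups. There are 60 or 120 controls. There is no true group effect.

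**Formulas.** Spurious shift = b × d. SE = s × √(1/n₁ + 1/n₂). Noncentrality λ = shift / SE. The false-positive rate is the probability that a noncentral t with n₁ + n₂ − 2 degrees of freedom exceeds the two-sided 5% limits.

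**Central case, b = 0.6 and d = 3.** Shift = 0.6 × 3 = 1.8 g/day.
- 60 vs 60: SE = 8 × √(1/60 + 1/60) = 1.461; λ = 1.8 / 1.461 = 1.232; rate 23.1%.
- 60 vs 120: SE = 8 × √(1/60 + 1/120) = 1.265; λ = 1.8 / 1.265 = 1.423; rate 29.3%.

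**Allowing for age spread within groups.** The unadjusted test sees a larger SD than 8, because age varies within each group. With an assumed within-group PMA SD of 5 weeks, SD = √(8² + (0.6 × 5)²) = √73 = 8.54, about 7% larger. The rates become 20.8% and 26.3%. The central range is therefore about 21–29%.

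**Dependence on the age gap (s = 8).**

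| Gap in mean PMA | Slope 0.3 (60 / 120 controls) | Slope 0.6 | Slope 0.9 |
|---|---|---|---|
| 0 weeks | 5% / 5% | 5% / 5% | 5% / 5% |
| 1 week | 5.5% / 5.6% | 6.9% / 7.6% | 9.4% / 10.9% |
| 3 weeks | 9.4% / 10.9% | 23.1% / 29.3% | 45.0% / 56.5% |

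**Does adjustment remove it?** A separate simulation (60 vs 60, no true effect, 4,000 runs per cell) worked in SD units. Age gaps were 0.25, 0.5 and 1.0 SD, and the correlation of growth with age was 0.3, 0.5 and 0.7 in absolute value. The unadjusted t-test rejected in 7% to 97% of runs. For a gap of 0.5 SD the rates were 14%, 28% and 48%. With age as a covariate the rate was 4.3% to 5.3% in every cell. The simulation assumes that age is measured and acts linearly, so it shows what adjustment can do under a correct model.

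**The case against.** The strongest reply is that this is silence rather than a specified error, and that several tempting readings go beyond the text. Much of that is right.

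- A reader might infer that the plan compares a raw rate in g/day. The text does not say so. A relative rate or a z-score change would also fit.
- A reader might infer that growth is measured to discharge or 4 weeks, so that rates over a few days count as much as rates over a month. That window belongs to the primary endpoint. The phrase about 1 year may govern growth velocity as well as feeding. If so, assessment at a common age would remove much of the problem of PMA at entry, though gestational age and starting size would still be unadjusted.
- A reader might infer that study and control infants do differ in age. No ages are given for either group. Both come from one centre and both needed a VFSS, so balance is possible, and with no gap there is no inflation.
- A reader might cite a much larger error. A 4-week gap at the steepest slope with 120 controls gives about 81%, but that rests wholly on assumed extremes, and an assumed age spread of 5 weeks lowers it to 69%.
- A reader might call any preterm against term growth difference spurious. Describing that difference may be the purpose of the objective, and section 16.1 assigns it no test.
- The t-test sentence is limited to the historical-control comparison, which section 3.3 describes as being on feeding outcomes. Growth falls under it only through the general wording on continuous variables.

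These points limit the claim but do not remove it. Growth velocity is a named endpoint, every method that section 16.1 offers for continuous variables is unadjusted as written, and no other section supplies an age or size term.

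**Conclusion.** The concern holds in this form: the metric is undefined and the planned comparisons are unadjusted, so any imbalance in PMA, gestational age or baseline size would confound growth. Whether such an imbalance exists between study and control infants is unknown. A difference in gestation is certain only for preterm against full term, where it defines the groups. The error rates above illustrate the mechanism and are not estimates for this study, because slope, SD, age gap and number of controls are all assumed. Growth velocity is a secondary endpoint with no power claim attached, and the primary endpoint is not touched by this point. The change is still worth making, because following the plan as written means an unadjusted test of an age-dependent outcome in groups that were not randomised.

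**What to change.** In section 6.1, state the metric for weight, length and head circumference and the window (in hospital or to 1 year). Say whether the reference to 1 year applies to growth velocity.

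In section 16.1, replace the unadjusted comparison of growth with a regression or mixed model, adjusted for PMA at VFSS and baseline size. Change in sex- and age-specific z-score is the preferred outcome. A mixed model can use whatever measurements are charted for each infant. For preterm against full term, name the test and use z-scores at corrected age, since gestation defines those groups. Report PMA, gestational age and size at VFSS by group, so that the reader can see any imbalance.

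The age limits in sections 6.1 and 9.1 are worded differently and must be reconciled, because they set the age range over which growth is compared.

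The cost is the z-score conversion, some model wording and a little analysis time. One limit should be stated: weekly charting is described as NICU routine, and the documents do not show that outpatients or discharged infants have serial length and head measurements. Those infants will contribute fewer points.

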- Three references are attached below in this section that lend support to our investigations, difficulties with strict protocols and need for personalization and parent preferred pragmatic therapies. Complimentary protocols (feeding outcomes in dysphagia, mechanisms of dysphagia, outcomes in gastrostomy bound infants) will address the original study aims as well. Updated statistical procedures based on the advice of our statistician, [name], PhD, DSMB team, and our Program Project Group is shown below.

3.3 Updated statistical procedures:

- The design of the Patient Preferred Trial has been modified to a single arm observational study with patients who have not achieved PO at the time of study or PO with feeding difficulties, comparing VFSS and manometry vs VFSS only (the historical control) on feeding outcomes. The primary outcome is success rate at discharge. We will prospectively follow 60 infants who are not fully PO or PO and symptomatic at the time of study. Based on our Feeding Outcomes of Dysphagia Study (vs. historical control), the success rate at discharge is around 60%. With 60 patients enrolled, we will have 90% power to detect an absolute increase of 20% from 60% for those who do not have treatment informed by manometry (historical control) to 80% in those in the manometry informed group with two-sided type I error of 0.05. Achievement will be assessed by tracking feeding methods at discharge or 4 weeks whichever is earlier and then at 1 year.
- [name], Peng J, Moore R, Saavedra J, Shepherd E, Fernandez S, Erdman SH, DiLorenzo C. Impact of personalized feeding program in 100 NICU infants: pathophysiology-based approach for better outcomes. *J Pediatr Gastroenterol Nutr.* 2012 Jan;54(1):62-70.
- [name], Stoner E, Gupta A, Bates DG, Fernandez S, Di Lorenzo C, Linscheid T. Evaluation and management of neonatal dysphagia: impact of pharyngoesophageal motility studies and multidisciplinary feeding strategy. *J Pediatr Gastroenterol Nutr.* 2009 Feb;48(2):186-92
- [name], Khot T, Moore R, Malkar M, Gulati IK, Slaughter JL. Feeding Methods at Discharge Predict Long-Term Feeding and Neurodevelopmental Outcomes in Preterm Infants Referred for Gastrostomy Evaluation. *J Pediatr.* 2017 Feb;181:125-130

3.4 Scientific or scholarly background for, rationale for, and significance of the research based on the existing literature and how will it add to existing knowledge

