- Removal and management of subject(s) from protocol: The investigator and/or the parent(s) have the right to withdraw from study at any time and opt for the standard of care. Parent(s) that withdraw their infants from the study therapy will be encouraged to continue to remain in the study for all follow up evaluations. Those who choose complete withdrawal from the study will be encouraged to follow the standard of care; wherein, response failures are followed until 1st birthday in the multidisciplinary developmental follow-up clinic.
- Intermediate outcome measures (up to 1 yr age): Acquisition of feeding and GI milestones during first year of life.

6.2 Describe:

- Manometry methods have been used concurrent with video, submental EMG, RIP, ECG, pulse-oximetry and nasal air flow to test basal and adaptive pharyngo-esophageal reflexes and sensory-motor characteristics of motility and to monitor safety. Concurrent synchronized video recordings will be performed to further validate symptoms based on objective definition of the esophageal reflexes. Documentation of symptom markers can be validated by integrating manometry with respiratory inductance plethysmography and video.
- Multimodal esophageal and pharyngeal sensory-motor testing protocols: We have developed and extensively used these protocols to measure sensory-motor characteristics of

PROTOCOL TITLE: Neonatal Esophagus and Airway Interactions in Health and Disease: Mechanisms and Management of Infant Dysphagia

reflexes, and these testing protocols will be performed as validated and reported

- The source records that will be used to collect data about subjects will be EPIC records, patient diary logs for symptoms, feeding process, medication compliance, physician visits and clinical data.

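### The plan does not require the symptom part of the primary endpoint to come from the same records, or follow the same definition, in study infants and historical controls

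*Combined protocol and SAP*

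**What the plan says.** Section 6.1 sets the endpoint: "Primary endpoint is therapeutic success defined as full oral feeding without symptoms requiring intervention at 4 weeks", or at discharge if that is earlier; the 4-week time point is for outpatients and infants still admitted. Section 4.1 carries the same symptom condition.

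Two other sections describe the outcome more narrowly. Section 2.1 gives success the symptom condition but defines failure only as a need for tube feeding. Section 3.3 says achievement is assessed by following how the infant is fed, and does not mention symptoms.

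On sources for study infants, section 6.2 states: "The source records that will be used to collect data about subjects will be EPIC records, patient diary logs for symptoms, feeding process", and goes on to medication compliance, physician visits and clinical data. Section 6.3 says feeding and growth outcomes come from parents as well as from medical records.

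On the controls, section 6.1 says they come from the same center and had VFSS with provider recommendations. It adds: "Control subjects did not require consent as they were historical controls". Section 3.3 gives their rate: "Based on our Feeding Outcomes of Dysphagia Study (vs. historical control), the success rate at discharge is around 60" per cent. No section states which records that rate came from, or whether it applied the symptom condition.

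Under the confounding safeguards in section 6.1, the plan notes "It is NICU standard to document in EPIC" symptoms and feeding methods daily. Section 16.1 compares study infants with controls by a chi-squared or Fisher's exact test.

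**The concern.** The primary hypothesis rests on one contrast: the success rate in 60 study infants against the rate in historical controls. That contrast is interpretable only if a given infant would be classified the same way in either group. The plan lists symptom diaries and parent report for one group and nothing for the other, and no rule ties the two to a common record, abstraction form or look-back period.

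The definition is also open. An infant on full oral feeds who still has symptoms needing intervention is not a success under section 6.1, is not a failure under section 2.1, and would pass on feeding method alone under section 3.3. If the 60% counted feeding method only, the groups differ in definition as well as in source.

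A measurement difference of this kind coincides exactly with group membership, so covariate adjustment cannot remove it. Section 16.1 plans none for the between-group test in any case.

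**Working it through.** **Inputs from the plan (section 3.3).** "We will prospectively follow 60 infants who are not fully PO or PO and symptomatic at the time of study". "With 60 patients enrolled, we will have 90% power to detect an absolute increase of 20% from 60" per cent "to 80% in those in the manometry informed group with two-sided type I error of 0.05". So n = 60, p0 = 0.60, p1 = 0.80 and two-sided alpha = 0.05 (0.025 in the upper tail). The number of controls is not given.

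**Step 1: reproduce the stated 90% power.** The figure corresponds to a one-sample test against a fixed 60%.

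- Exact binomial rule: take the smallest r with P(X ≥ r | 60, 0.60) ≤ 0.025. At r = 43 the tail is 0.0413; at r = 44 it is 0.0221. The rule is at least 44 successes.
- Exact power: P(X ≥ 44 | 60, 0.80) = 0.9228, or 92.3%.
- Normal approximation: Φ{[(p1 − p0)√n − 1.96√(p0(1 − p0))] / √(p1(1 − p1))} = Φ{[0.20 × 7.746 − 1.96 × 0.490] / 0.40} = 93.0%. With a continuity correction of 1/(2n) it is 90.5%.

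The stated power is reproduced.

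**Step 2: add a measurement shift.** Let b be the change in the recorded study success rate that arises only because study infants are measured differently from the controls. The documents give no value, so b is assumed at 2, 5 and 10 points. With 60 infants, 5 points is 60 × 0.05 = 3 infants.

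| Assumed shift b | Power at true 80%: P(X ≥ 44 given 0.80 + b) | False-positive chance at true 60%: P(X ≥ 44 given 0.60 + b) |
|---|---|---|
| −10 points | 34.2% | below 0.1% |
| −5 points | 68.0% | 0.3% |
| −2 points | 84.8% | 1.0% |
| 0 | 92.3% | 2.2% |
| +2 points | 96.7% | 4.5% |
| +5 points | 99.4% | 11.0% |
| +10 points | above 99.9% | 34.2% |

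The two 34.2% entries agree because 0.80 − 0.10 and 0.60 + 0.10 are both 0.70.

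**Step 3: is the direction known?** Both signs are plausible.

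- Downward: diaries record symptoms needing intervention that the chart lacks, or the 60% was counted on feeding method alone while study infants must also meet the symptom condition.
- Upward: parents, who see the manometry results and choose the therapy (section 7.1), under-report symptoms.

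Nothing in the documents settles which of these would dominate.

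**Step 4: does a common source exist?** For NICU inpatients it probably does: section 6.1 describes daily charting of symptoms and feeding as standard, and the controls come from the same center. For outpatients scored at 4 weeks, no equivalent routine symptom record is described, and their share of the 60 is not given.

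**The case against.** The strongest reply is that the sentence in section 6.2 is a general list of source records and assigns none of them to an endpoint. The one sentence on how achievement is assessed, in section 3.3, points to feeding method. The endpoint counts only symptoms that required intervention, and these are more likely than mild ones to leave a clinical record, so diary-only symptoms might reclassify few infants. Daily charting also offers a shared source for inpatients. These points stand.

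They limit what can be claimed. A reader might infer that diaries decide the endpoint in study infants, that controls were scored from charts alone, and that the study rate is therefore biased downward. The documents support none of this as fact. No section says diaries feed the primary endpoint. The controls' source is not stated, so chart-only is an inference from their being historical and unconsented. Nor is there evidence on the direction. It would also go too far to say that outpatients depend on the diary, since section 6.2 lists EPIC and physician visits too.

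The reply does not close the gap. Diaries are listed specifically for symptoms, symptoms are part of the endpoint, and nothing excludes the diaries from it. A shared chart source helps only if the plan requires it to be used. The check by two team members in section 16.3 verifies data but does not align sources between groups.

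**Conclusion.** The concern holds as a gap in the plan. As written, it allows the study success rate and the historical 60% to come from different sources, and possibly different definitions, so like-for-like measurement cannot be confirmed. It does not show that a bias is present or which way it would run.

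The possible size is material. A difference of about 3 infants in 60 is enough to take power from 92.3% to 68.0%, or the false-positive chance from 2.2% to 11.0%. These figures rest on two assumptions: the size of the shift, for which the documents give no basis, and a fixed 60% comparator, which matches the sample-size statement but not the two-group test in section 16.1.

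**What to change.** In sections 6.1 and 6.2:

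1. State that the primary endpoint is classified in both groups by one written definition, from EPIC or other medical records only, with one abstraction form and the same look-back before discharge or 4 weeks. Bring sections 2.1 and 3.3 into line with it. Where possible, keep abstractors unaware of group.
2. Confirm that the 60% control rate uses that definition and time point. If it does not, re-abstract it.
3. Use diaries and parent reports only for description within the study group and for a sensitivity analysis of the primary result.
4. Report the inpatient-only comparison alongside the full one, because daily symptom charting is described only as a NICU standard.

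The cost is protocol wording plus abstraction from a record that already exists at the same center; no new data collection is needed. The price is that diary detail is lost from the primary endpoint, and outpatient chart data may be sparser.
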